6 ENDPOINTS AND COVARIATES

The following Primary end points and Secondary end points will be identified with appropriate diagnosis codes. The detailed list of diagnosis codes in each country is available in a separate document.

6.1 EFFICACY/ EFFECTIVENESS ENDPOINT(S)

Not applicable

6.2 SAFETY ENDPOINTS

All the primary and secondary endpoints are safety endpoints (see below).

Primary Endpoints

- Venous thromboembolism (VTE) defined as deep vein thrombosis (DVT), pulmonary embolism (PE), retinal vein thrombosis, and sinus thrombosis

Secondary Endpoints

- Ischemic Stroke
- Thrombotic/Ischemic Cardiac Disorders (including myocardial infarction, myocardial ischemia and coronary occlusion)
- Atrial Fibrillation
- Hypertriglyceridemia

- Biliary Events: Cholecystitis, cholelithiasis
- Clinical Fractures
- Chronic/Acute Renal Failure (including chronic renal insufficiency and end stage renal disease)
- Depression
- Selected ocular events including retinal vascular occlusions, disorders of the globe, iris, ciliary body, retina, eye adnexa and cornea.
- Thyroid disorders
- Aggregate of all malignancies including Breast, Renal, Thyroid, Ovarian, Gastrointestinal tract, Lung cancer
- Malignancies of Breast
- Malignancies of Kidney
- Malignancies of Thyroid
- Malignancies of Ovary
- Malignancies of Gastrointestinal tract
- Malignancies of Lung

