### **2.1.2. Secondary Objective**

To estimate and compare the incidence rates of VTE among women receiving bazedoxifene and women receiving raloxifene for treatment of osteoporosis.

To estimate and compare the incidence rates of selected clinical endpoints (listed as secondary endpoints in section “2.2 Endpoints”) among women receiving bazedoxifene and women receiving a bisphosphonate for treatment of osteoporosis.

To estimate and compare the incidence rates of selected clinical endpoints (listed as secondary endpoints in section “2.2 Endpoints”) among women receiving bazedoxifene and women receiving raloxifene for treatment of osteoporosis.

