## **2.2. Endpoints**

The clinical endpoints for this study were determined based on the clinical and pre-clinical data from the bazedoxifene development program, class effects of other SERMs, and recommendations of the EU Rapporteurs.

Potential endpoints will be identified by an electronic search of the coded diagnosis fields of the medical records. The relevant diagnostic codes that will be used as operational definitions of each of the endpoints will be listed in the statistical analytic plan of the study. The available medical record of the identified cases for the primary endpoint will be retrieved and reviewed to confirm the diagnosis.

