## 7. DATA ANALYSIS/STATISTICAL METHODS

The details of the data analysis will be documented in a Statistical Analysis Plan (SAP) document, which will be maintained by the sponsor. The SAP will elaborate, and may modify the analytic plans outlined in the protocol; however, any major modifications will be reflected in a protocol amendment.

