1 AMENDMENTS FROM PREVIOUS VERSION(S)

Version	Date	Summary of Changes/Comments
Version 1.0	18-November-2013	Not Applicable
Version 2.0	27-September-2016	Administrative changes. Updated SAP format to reflect CT24-GSOP-SD-GL04 Non-interventional (NI) Study Statistical Analysis Plan Template Version 1.0, Date 31-Dec-2013.

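### The SAP lists a thyroid-disorders endpoint where the protocol lists goitre, so no goitre-specific incidence rate or hazard ratio is planned

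*SAP*

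**What the plan says.** Protocol 2.2.2 ends its list of secondary endpoints with goitre. The secondary objectives in protocol 2.1.2 apply to every endpoint on that list: "To estimate and compare the incidence rates of selected clinical endpoints", once against bisphosphonate and once against raloxifene. Protocol 2.2 says the endpoints were chosen from "clinical and pre-clinical data from the bazedoxifene development program, class effects of other SERMs, and recommendations of the EU Rapporteurs".

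SAP 6.2 does not list goitre, and the word appears nowhere in the SAP. The list has "Thyroid disorders" instead. It carries "Malignancies of Thyroid" as a separate item, so the new entry is not a renaming of the protocol's thyroid cancer endpoint. No reason is given.

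On codes, protocol 2.2 says that the diagnostic codes defining each endpoint "will be listed in the statistical analytic plan of the study". SAP section 6 points elsewhere: "The detailed list of diagnosis codes in each country is available in a separate document".

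Protocol section 7 lets the SAP elaborate and modify the analysis plan, and adds that "any major modifications will be reflected in a protocol amendment". The protocol text supplied still says goitre.

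**The concern.** A goitre endpoint and a thyroid-disorders endpoint answer different questions. Goitre is one named condition on a list chosen for stated safety reasons, in a study that is a commitment to the regulator. Read at face value, thyroid disorders is a wider class that includes goitre among other conditions.

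At stake is whether the study report will contain the goitre result that the protocol calls for. If the wider reading is right, three things follow for this endpoint:

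- Events other than goitre enter the numerator.
- A woman with any earlier thyroid diagnosis, not only goitre, is removed from the incident-case analysis under SAP 5.4.
- A non-goitre thyroid event ends her follow-up for this endpoint under SAP 2.1 and 8.1.2, so a later goitre is not counted.

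A real goitre effect could then be hidden in a composite ratio near 1.

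**Working it through.** **1. Is goitre estimated anywhere in the SAP?** Three places were compared.

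- Protocol 2.1.2 with 2.2.2: goitre is to be estimated and compared against both comparators.
- SAP 6.2: goitre is absent, and thyroid disorders and thyroid malignancy are separate items.
- SAP 2.2 (secondary objectives 2 and 3) and SAP 8.2.5 (analysis summary): both cover the secondary endpoints, which SAP 2.2 defines by reference to section 6.

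No goitre-specific rate or hazard ratio is therefore planned. This step needs no assumption.

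**2. What would a wider code set do to the ratio?** The documents give no rate, sample size or power for goitre or thyroid disease, so there is no figure of the plan's own to reproduce. What follows is illustration.

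Let g be the share of comparator thyroid events that are goitre, R the true goitre rate ratio, and r the rate ratio for all other thyroid diagnoses. For rare events,

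composite ratio = g × R + (1 − g) × r.

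Assume R = 2 and r = 1, meaning the other diagnoses are unrelated to treatment. The formula becomes 2g + (1 − g) = 1 + g.

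| Assumed g | Composite ratio |
|---|---|
| 10% | 1 + 0.10 = 1.1 |
| 30% | 1 + 0.30 = 1.3 |
| 50% | 1 + 0.50 = 1.5 |
| 100% (goitre codes only) | 2.0 |

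The result depends on r. With g = 30% and r = 1.5, the composite is 0.3 × 2 + 0.7 × 1.5 = 1.65. With r = 2 there is no dilution.

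**3. Could the extra events make up for the dilution?**

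- Inputs from the documents: 1,823 bazedoxifene and 10,938 bisphosphonate women (SAP 5.4), up to 5 years of follow-up and 15% annual loss (protocol 7.1), two-sided 0.05 (SAP 4.2).
- Person-years per woman: (1 − 0.85^5) / (−ln 0.85) = 3.42, or about 6,240 and 37,440 in the two groups. History exclusions are ignored.
- Assumed inputs: a comparator goitre rate of 2 per 1,000 person-years, R = 2 and r = 1.
- Power is Φ(ln(ratio)/SE − 1.96), with SE = √(1/e1 + 1/e2), where e1 and e2 are the expected events with bazedoxifene and bisphosphonate.

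Goitre alone: e1 = 6,240 × 0.002 × 2 = 25.0 and e2 = 37,440 × 0.002 = 74.9. SE = 0.231, and ln 2 / 0.231 = 3.00, so power is Φ(1.04), about 85%.

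g = 50%: the total comparator rate is 4 per 1,000, so e1 = 37.4 and e2 = 149.8. SE = 0.183, and ln 1.5 / 0.183 = 2.22, so power is about 60%.

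g = 10%: the total comparator rate is 20 per 1,000, so e1 = 137.3 and e2 = 748.8. SE = 0.093, and ln 1.1 / 0.093 = 1.03, so power is about 18%.

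With assumed goitre rates of 1 to 4 per 1,000, the three ranges are 56% to 99%, 35% to 88%, and 11% to 31%. Under these assumptions the added events do not offset the dilution. The absolute figures are not estimates for this study.

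**The case against.** The strongest reply is that codes define an endpoint and labels do not, and the code list is not among the documents. SAP 8.1.1 says the sponsor has validated the codes for each endpoint. The SAP also rewords other protocol endpoints: fractures become clinical fractures, and renal cancer becomes malignancies of the kidney. Its labels are therefore an imperfect guide to code content. If the list holds only goitre codes, there is no wider count, no dilution and no larger history exclusion, and the fault is one of labelling. This stands, and it makes the consequences conditional. It does not remove the mismatch: nothing in the SAP narrows the label, and the protocol said the codes would be in the SAP.

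It is also fair that every number above rests on assumed shares, rates and ratios, and that dilution requires the other thyroid diagnoses to be unrelated to treatment. The documents neither support nor exclude that.

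Three stronger readings are tempting, and the documents do not support them.

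- **An unrecorded switch.** A reader might infer this from the SAP change log, whose version 2.0 entry opens "Administrative changes. Updated SAP format to reflect" and mentions no endpoint change. That entry covers only the step from SAP version 1.0 to 2.0. If version 1.0 already said thyroid disorders, the entry is correct. Version 1.0 is not supplied, so the log shows nothing about when the change arose.
- **A breach of the amendment rule.** The same sentence of the protocol allows the SAP to modify the plan, and only major changes need an amendment. Major is not defined. Whether one of many secondary endpoints qualifies is a judgement.
- **Women with a thyroid history are lost to the study.** SAP 5.4 excludes them only from this endpoint's incident-case analysis. They are analysed separately and stay eligible for the other outcomes.

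**Conclusion.** The concern holds in a limited form. The protocol and SAP name different thyroid endpoints without explanation, and the SAP as written plans no goitre-specific estimate. That follows from the text alone.

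The wider event count, the wider history exclusion and the earlier end of follow-up hold unless the separate code list restricts the endpoint to goitre. Dilution towards 1 further requires that the other diagnoses be unrelated to treatment. With an assumed true ratio of 2, the composite would then be 1.1 to 1.5 for assumed goitre shares of 10% to 50%.

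The point is minor. It affects one secondary safety endpoint and leaves the VTE objective and the other listed endpoints as they are. It is worth correcting because a protocol endpoint would otherwise go unreported as such.

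**What to change.** List goitre in SAP 6.2 as a secondary endpoint with its own code list and its own prior-history exclusion. Keep thyroid disorders, excluding thyroid malignancy, only as an additional endpoint if it is wanted.

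Check the separate code list first. If it already holds only goitre codes, change the label to goitre and nothing else is needed. If goitre cannot be separated in one country's coding, for example because of the mapping between Italian and Spanish codes described in SAP 8.1, say so in the SAP and justify the broader endpoint in a protocol amendment.

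The cost is one endpoint line, a subset of codes and one more run of analyses already specified. No new data are needed.

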6.3 OTHER ENDPOINTS

Not Applicable

7 HANDLING OF MISSING VALUES

For each variable, the number and proportion of patients missing data for each treatment group will be specified. The primary analyses will be done using only the information available in the unmodified dataset. Smoking status, alcohol consumption, height and/or weight (BMI) values are known to be missing for approximately 40-60% patients in the Cegedim LPD based on previous studies. (Age of patients will always be known as it is a selection criterion). Dates are automatically recorded in the Cegedim LPD and doctors can select diseases codes from the pre-defined lists. In all analyses, if a condition (disease or treatment) other than the diagnosis of osteoporosis is not recorded, it will be assumed to be non-existent.

To estimate the effect of missing data, two additional analyses for the primary study endpoint will be conducted. First, the analyses will be repeated utilizing a dataset in which cases with missing values of main study covariates of BMI, smoking status and alcohol status are excluded. The disadvantage to this approach is the reduction in the sample size. Another disadvantage to this approach is that the subjects with missing values may be different than the subjects without missing values (e.g., missing values that are not missing at random), resulting in a non-representative sample after removing the cases with missing values. Second, multiple imputations for the missing values of BMI, smoking status, alcohol status will be used in the second set of analyses and compared to complete case analyses to understand the potential impact of missing data on results [2].

Outlier

Extreme values for weight and height will be searched for. If a value seems implausible, as regard to gender or ratio weight/height, it will be put as missing.

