Venous Thromboembolic Events (VTE) are defined as deep vein thrombosis, pulmonary embolism, retinal vein thrombosis, and venous sinus thrombosis. This objective is to compare this incidence in real life settings with validated diagnosis codes, ICD9 in Italy and International Classification of Primary Care (ICPC) codes in Spain.

The availability of medical history of all relevant medical diagnosis for patients will be checked in both the Spanish and the Italian database and presented if available. The variables of medical history (diabetes, hypertension, VTE and Malignancies) will be presented in classes (Yes/No) before index date. (All the detailed diagnosis codes of each endpoint have been validated by Pfizer and are available in a separate reference document). For all medical history and smoking status, if the relevant information is not found in the database, it will be assumed to be negative.

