- Previous history of major lower extremity (hip, knee) arthroplasty, arthroscopic surgery (information on arthroscopic surgery not available in Italian database)
- General surgery, major orthopedic surgery (<1month prior to incidence of VTE)
- (Information on general surgery not available in Italian database)
- Multiple trauma (<1month prior to incidence of VTE)
- Hip, pelvis, or leg fracture (<1month prior to incidence of VTE)
- Stroke (<1month prior to incidence of VTE)
- Acute spinal cord injury (paralysis) (<1month prior to incidence of VTE)
- Hormone replacement therapy (limited information available in both databases)

A Cox model will be used in order to take into account the time varying component. The time from the beginning of the treatment (one among three types, BZA, raloxifene, and bisphosphonate) to the occurrence of primary end point is fitted in this model. The Proportional Hazards (PH) assumption will be tested for each covariable. If the PH assumption does not hold for some covariates, the use of time-varying HR for those covariates will be explored. If a categorical variable with more than 2 levels does not satisfy this PH assumption, collapsing some categories will be attempted to satisfy the PH assumption. Correlations between variables will also be evaluated in order to find independent factors and a final model that is clinically relevant.

First, the univariate analysis will be carried out on each covariable in order to determine the explanatory variables to be included in the final multivariate model. All significant variables with a p -value ≤ 0.20 in the univariate model will be taken into account in the multivariate Cox model.

If > 80% of the important risk factors for VTE listed above does not satisfy the PH assumption, a logistic regression analysis would be performed instead of Cox model to otherwise determine if the covariable is related to the incidence primary endpoint (VTE). The dependent variable would be the incidence of the primary end point during the follow-up period categorized as a binary variable. The 2 indicators of treatment group (BZA vs. bisphosphonates, raloxifene, will be forced in the multivariate model (Cox model or logistic model) to analyze incidence in each class of treatment, adjusted on

significant factors. Hazard ratios (HR) (odds ratios (OR) in case of logistic regression) with 95% Confidence intervals (CIs) and p-values will be presented.

[figure not shown]
Patients Switching Medications

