8.2.5 SUMMARY OF STATISTICAL ANALYSIS

Analyses for Primary Objective and Secondary Objective 1

Comparator: BZA vs. bisphosphonate (primary objective), BZA vs. raloxifene (secondary objective 1).

Study endpoint: VTE.

Populations: a. Full BZA full raloxifene, random age stratified bisphosphonate subgroup
b. Incident user subgroup.

Statistical Method:

- i. Incidence rate, cumulative method (*Total new cases during follow-up period / Total persons at risk during follow-up period*) with stratification by risks of interest e.g. Age, BMI.
- ii. Univariate and multivariate incidence rate by incidence density (*Total new cases during follow up period / Total person years during follow-up period*)*1000) method using Cox regression model and a Likelihood Ratio Test for testing Hazard Ratio (HR) =1 (ratio of hazard in BZA population vs. bisphosphonate/raloxifene population) with covariates associated with VTE outcome and exposure (Drug groups).

Sensitivity analyses:

- i. Repeat analysis will be conducted that compares using a 30-day and a 90-day definition of recent exposure with using the 60-day definition.
- ii. Missing Data: First, the analyses will be repeated utilizing a complete dataset in which cases with missing values of main study covariates of BMI, smoking status and alcohol status have been deleted. Second, multiple imputation for the missing values of BMI, smoking status, alcohol status will be used in the second set of analyses.

Multiple imputation procedure:

- 1) Estimate distribution of BMI, smoking status and alcohol status according to patients whose data are available.
- 2) For the patients who had missing values those variables draw values of the variables from the distribution from 1).
- 3) With the imputed dataset (including none-missing data), estimate HR as described.
- 4) Repeat 2)-3) for m times, and record HR of each time.
- 5) Calculate mean of m estimates of HR.
- 6) Adjust variance of HR with the following formula, and use the variance to calculate confidence interval.

$$V = \left(1 + \frac{1}{M}\right) V_B + V_W.$$

V_B is the between imputation variance, and V_W is within imputation variance.

Analyses for Secondary Objective 2 and Secondary Objective 3

Comparator: BZA vs. bisphosphonate (secondary objective 2), BZA vs. raloxifene (secondary objective 3).

Study endpoint: Secondary endpoints.

Population: a. Full BZA, full raloxifene, random age stratified bisphosphonate subgroup.
b. Incident user subgroup

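### The SAP has no rule for women without BMI in the adjusted Cox model: if BMI passes the p ≤ 0.20 screen, the adjusted VTE hazard ratio may rest on only 40-60% of the cohort, and the complete-case check cannot show the effect

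*SAP*

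**What the plan says.** SAP section 7 sets the basis: "The primary analyses will be done using only the information available in the unmodified dataset". The same paragraph gives the scale of the gap: "Smoking status, alcohol consumption, height and/or weight (BMI) values are known to be missing for approximately 40-60% patients in the Cegedim LPD". The figure is attributed to previous studies in the database.

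SAP 8.1.4 and 8.2.4 both list BMI among the factors considered for the Cox model. Under 8.1.4, a factor with p ≤ 0.20 "in the univariate model will be taken into account in the multivariate Cox model". Only the treatment indicators are forced in. SAP 4.2 and 8.2.2 use the Cox hazard ratio to compare the treatment groups, and 8.2.5 lists univariate and multivariate Cox analyses for the primary objective.

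Two missing-data checks are planned. The first uses a dataset in which "cases with missing values of main study covariates of BMI, smoking status and alcohol status are excluded". The second is multiple imputation of the same three variables. Section 7 also promises the number and proportion missing for each variable by treatment group.

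For smoking, SAP 8.1.1 says: "For all medical history and smoking status, if the relevant information is not found in the database, it will be assumed to be negative". There is no corresponding rule for BMI.

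**The concern.** The plan does not fix which women contribute to the adjusted hazard ratio. A Cox model fitted to unmodified data leaves out, by software default, any woman with a missing covariate. Whether BMI is in the model depends on a p-value seen only at analysis, so the analysis set depends on it too. If BMI enters, three things follow.

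- The adjusted estimate loses about half of an already small number of events.
- The treatment-only and adjusted hazard ratios come from different women, so the change between them mixes confounding with a change of sample.
- The first missing-data check also excludes every woman without BMI, so comparing it with the adjusted model says nothing about the effect of missing BMI.

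Section 7 names a smaller sample and possible non-representativeness as drawbacks of the complete-case check only. The adjusted model would share both.

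**Working it through.** **Which of the three variables can remove a woman from the adjusted model**

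| Variable | In the Cox factor lists (8.1.4, 8.2.4)? | Rule if unrecorded | Removes women from the adjusted model? | Removes women from the complete-case check? |
|---|---|---|---|---|
| BMI | Yes, both | None | Yes, if it passes the screen | Yes |
| Smoking | Yes, subject to availability | Negative (8.1.1), but missing (7, 8.2.5) | No, under 8.1.1 | Yes, under 7 and 8.2.5 |
| Alcohol | Neither | Missing (7, 8.2.5) | No | Yes |

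**Inputs**
- 1,823 bazedoxifene women and 1,823 × 6 = 10,938 sampled bisphosphonate women (SAP 5.4).
- Comparator VTE rate 1.74 per 1,000 patient-years, up to 5 years of follow-up, 15% annual loss, Wald 95% intervals (Protocol 7.1).
- Missing BMI 40-60% (SAP 7). Equal missingness in both arms is assumed.
- Person-years per woman are not stated, so they were inferred from Protocol Table 3.

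**Formulas**
- Events: d = n × person-years × 0.00174 (× IRR in the bazedoxifene arm).
- SE(log IRR) = √(1/d1 + 1/d0).
- 95% CI = IRR × exp(±1.96 × SE).
- Power ≈ Φ(ln IRR / SE − 1.96).

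**Reproducing Protocol Table 3, 1:6 row (1,750 : 10,500)**

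With 5 × 0.85 = 4.25 person-years per woman, d0 = 10,500 × 4.25 × 0.00174 = 77.65, and d1 = 12.94 at IRR 1. The intervals are 0.56-1.80, 0.91-2.47 and 1.28-3.12 at IRR 1, 1.5 and 2. The table prints 0.6-1.8, 0.9-2.5 and 1.3-3.1, so all six limits match. Across the whole table 22 of 24 limits match. Compounding the 15% loss gives 3.42 person-years and does not reproduce the row (1.22-3.28 at IRR 2).

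**Applying it to the SAP cohort at IRR 2**

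With all women, d1 = 1,823 × 4.25 × 0.00174 × 2 = 27.0 and d0 = 10,938 × 4.25 × 0.00174 = 80.9, so SE = √(1/27.0 + 1/80.9) = 0.222. If a fraction f of women is kept, SE becomes 0.222/√f.

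| BMI missing | Women kept | Events (d1 + d0) | 95% CI | Power |
|---|---|---|---|---|
| None | 1,823 : 10,938 | 27.0 + 80.9 | 1.29-3.09 | 88% |
| 40% | 1,094 : 6,563 | 16.2 + 48.5 | 1.14-3.51 | 68% |
| 50% | 912 : 5,469 | 13.5 + 40.4 | 1.08-3.70 | 60% |
| 60% | 729 : 4,375 | 10.8 + 32.4 | 1.00-3.98 | 51% |

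With 3.42 person-years instead, the interval goes from 1.23-3.25 (none missing) to 1.07-3.74 (40%) or 0.93-4.31 (60%). The pattern is the same.

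**Size of the complete-case check**

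This depends on joint missingness, which the documents do not give. Assume the same missing fraction for each variable.
- Complete overlap: 40-60% of the cohort is kept, the same women as in the BMI-adjusted model.
- Independence, three variables: 0.6³ = 21.6% down to 0.4³ = 6.4%.
- Independence, with unrecorded smoking coded negative: 0.6² = 36% down to 0.4² = 16%.

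In every case the set lies inside the women with BMI recorded.

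**The case against.** The strongest reply is that the loss is neither written nor certain. The SAP nowhere says that women without BMI are deleted. BMI enters only if it passes the screen, and section 7 presents the dataset without incomplete cases as an additional analysis, which suggests that the authors did not intend it as the main one. SAP 8.1.2 labels cumulative incidence as primary, 8.2.4 calls time-to-event secondary, and Protocol 7.2 makes a regression model optional, depending on data completeness. All of this stands, and it makes the loss conditional. It does not supply the missing rule, and the Cox hazard ratio remains the stated comparison.

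A reader might infer more than the documents support:

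- That the study's headline result loses half the cohort. Cumulative incidence, crude rates, the treatment-only hazard ratio and any adjusted model without BMI keep all women.
- That the loss would be silent. Missing counts by variable and arm are promised. What is not required is N and events for each fitted model.
- That the complete-case check largely repeats the adjusted model. That holds only if missingness overlaps; otherwise the check is much smaller. What holds in every case is that it cannot reveal the effect of missing BMI.
- That BMI is recorded selectively and the hazard ratio is therefore biased. Section 7 says only that women with missing values may differ, and missing covariate values alone do not bias a complete-case hazard ratio.
- That the planned imputation can simply be promoted. As written in 8.2.5, it draws from the observed distribution without mention of treatment, event or other covariates.

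**Conclusion.** The point holds in conditional form. The SAP does not say how women without BMI enter the adjusted Cox model. If BMI passes p ≤ 0.20 and software defaults apply, the adjusted VTE hazard ratio rests on about 40-60% of the cohort. At a true ratio of 2 the lower confidence limit falls from 1.29 to between 1.14 and 1.00, with power near 88% falling to between 68% and 51%. The precision of Protocol Table 3, on which SAP 5.4 relies for its 1:6 sampling, would not carry over to the adjusted comparison.

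The size rests on three assumptions: equal missingness by arm, 4.25 person-years per woman, and the 40-60% figure applying here. That figure comes from earlier studies, and SAP 8.2.1 allows the nearest available height and weight to be used, so BMI may be more complete in this cohort.

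Two faults do not depend on the screen. The complete-case rule deletes women for alcohol, which is not a listed Cox factor. Unrecorded smoking is negative in 8.1.1 but missing in 7 and 8.2.5.

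**What to change.** Amend SAP 7, 8.1.4 and 8.2.5 as follows.

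1. Make an analysis that keeps all women the main adjusted hazard ratio. Either use multiple imputation with an imputation model that includes treatment, event indicator, follow-up time and the other Cox covariates, replacing the draw now described in 8.2.5; or prespecify a main model without BMI and add BMI in the imputed analysis.
2. Report the treatment-only and adjusted hazard ratios on the same women, with N and events for each model.
3. Keep the complete-case analysis as a sensitivity analysis, defined only on covariates in the model, and drop alcohol from its deletion rule. Compare the imputed result with the main model, not only with the complete-case result.
4. Reconcile 8.1.1 with 7 and 8.2.5 on unrecorded smoking.

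No new data are needed. The cost is some extra analysis work and, for the imputed estimate, reliance on a missing-at-random assumption, which the SAP should state.
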